3. INVESTIGATIONAL PLAN

3.1 General Schema of Study Design

Patients with previously untreated osteosarcoma will receive 6 cycles of the standard MAP (Methotrexate, Adriamycin [doxorubicin], cisPlatin) chemotherapy regimen. The first two cycles will be administered neoadjuvantly followed by surgical resection of the primary tumor if

Protocol number: CHP12ST051
Amendment number:
Version date: April 2, 2013

feasible, and then 2 additional cycles of MAP followed by 2 cycles of MA (Figure 2). A randomized, 2 x 2 factorial, crossover design (see Study Diagram) will be used to:

- study the effect of prolonging the methotrexate infusion duration from 4 h to 12 h on nephrotoxicity as measured by biomarkers of acute renal injury and
- study the effect of the OCT2 inhibitor, pantoprazole, on cisplatin nephrotoxicity as measured by biomarkers of acute renal injury and on ototoxicity as assessed on serial audiograms.

Each patient will serve as his/her own control, and 24 evaluable patients will be studied. Randomization to one of 4 treatment arms (see Study Diagram) will be performed after enrollment onto the trial and prior to the start of neoadjuvant chemotherapy. The use of sensitive, short-term biomarkers as endpoints to assess the effect of these interventions, continuous (rather than categorical) endpoints analyzed by dose, course or treatment cycle rather than by patient, and a cross-over design that allows patients to serve as their own controls will minimize the number of subjects and time required to complete this pilot study, increase the statistical power, and maximize the amount of data collected.

3.1.1 Screening, Diagnosis, and Staging

Patients with osteosarcoma typically present to the orthopedic or oncology clinical service with a history of pain and swelling at the primary tumor site and radiographic evidence of a destructive bone lesion. The standard of care at CHOP is to perform an open biopsy to ensure that an adequate amount of viable tumor tissue is obtained to make a diagnosis. **Histological diagnosis** is based on morphology and the presence of osteoid (unmineralized bone matrix). There are no specific immunohistochemical stains that can be used to confirm the diagnosis of osteosarcoma.

The standard radiographic **staging** for osteosarcoma to assess tumor extent in the involved bone and to document the presence of overt metastatic disease in the lungs or skeleton includes:

- AP and lateral radiographic of the entire involved bone
- MRI with contrast of the entire involved bone, including joints proximal and distal to the tumor (e.g., for a distal femoral tumor, the scan should include the entire femur with the hip and knee joints)
- Chest CT scan
- ^{99m}Tc -MDP Bone scan OR ^{18}F FDG PET scan

Other standard clinical and laboratory test performed prior to initiation of treatment in patients with osteosarcoma include:

- History and physical examination, including measurement of the primary tumor (circumference for limb tumors) and performance status,
- CBC with differential, comprehensive mineral panel, calcium, phosphate, magnesium,

Protocol number: CHP12ST051
Amendment number:
Version date: April 2, 2013

urinalysis, 12-24 h urine collection for creatinine clearance, urine pregnancy test,

- Echocardiogram with quantitation of left ventricular shortening fraction prior to administration of doxorubicin, and
- Audiogram to document baseline hearing prior to administration of cisplatin.

These procedures are standard of care for patients with osteosarcoma and can be performed prior to informed consent and enrollment on this clinical trial. Results of these studies will be used as baseline values and entered into the clinical trial database after patients have consented and enrolled onto the trial.

3.1.2 Baseline (Pretreatment) Research Studies

See Section 4.1 for research sample collection, processing, and storage instructions.

- Urinary AKI Markers (NAG, NGAL, KIM-1)
- Plasma and urine magnesium and creatinine for FEMg.
- Serum cystatin C
- Serum bone-specific alkaline phosphatase (BSAP)
- Plasma pre-albumin
- Patient-reported outcomes survey
- Upper arm (mid-way between the shoulder [acromion] and elbow [humeral lateral condyle]) circumference with elbow extended and triceps skin fold thickness 1 cm above site circumference was measured in arm NOT involved with tumor. These measurements are performed to estimate nutritional status, muscle mass, and creatinine production.

3.1.3 Treatment with MAP Regimen

All patients will receive 6 cycles of the 3-drug MAP chemotherapy regimen (Methotrexate, Adriamycin [doxorubicin] and cisPlatin) that is shown in Figure 2. Cycles 1 & 2 will be administered neoadjuvantly (before resection of the primary tumor). After recovery from surgery, patients will resume treatment with 2 cycles of MAP followed by 2 cycles of MA (no cisplatin).

Treatment arm specific treatment delivery maps (TDM) will be generated for each patient after randomization and placed in the clinic chart to serve as a guide. Appendix 1 shows an example of a TDM.

Standard treatments: Cycles 1-4 of MAP are 5 weeks (35 days) in duration. Cisplatin and doxorubicin are administered on days 1 & 2 and HDMTX + leucovorin rescue is infused on days 22 & 29. cisplatin is not administered in Cycles 5 & 6 and the duration of Cycles 5 & 6 is 4 weeks (28 days). During cycles 5 & 6, doxorubicin is administered on days 1 & 2 and HDMTX + leucovorin rescue is infused on days 15 & 22. Supportive care/rescue agents that are administered with MAP to alleviate toxicity include antiemetics (see CHOP Cancer Center

Protocol number: CHP12ST051
Amendment number:
Version date: April 2, 2013

antiemetic guidelines), dexrazoxane as a cardioprotectant, pegfilgrastim to facilitate neutrophil recovery after doxorubicin, and leucovorin as a HDMTX rescue agent. Intravenous fluid hydration is administered with cisplatin and HDMTX to prevent nephrotoxicity, and urine alkalinization is used to increase the solubility of MTX in urine.

Research Interventions: Pantoprazole will be administered intravenously with cisplatin on 2 consecutive treatment cycles (either Cycles 1 & 2 or Cycles 3 & 4), and the order of pantoprazole administration will be determined by randomization (see Study Diagram). Patients will receive HDMTX as 4 and 12 h infusions on 2 consecutive treatment cycles (Cycles 1 & 2 or Cycles 3 & 4), and the order of the infusion durations will be determined by randomization.

Drug doses, schedules, and administration routes: for the chemotherapy and supportive care/rescue medications are listed below:

- **Dexrazoxane** 375 mg/m²/dose IV over 15 min immediately prior to the doxorubicin doses on days 1 & 2 (total dose 750 mg/m²/cycle) of treatment cycles 1-6;
- **DOXOrubicin** 37.5 mg/m²/dose IV over 15 min on days 1 & 2 (total dose 75 mg/m²/cycle) of treatment cycles 1-6 (total cumulative dose 450 mg/m²);
- **Pantoprazole** 0.3 mg/kg IV over 15 min immediately prior to cisplatin as a loading dose on days 1 & 2 followed by 1.3 mg/kg IV infused over 4 h concurrent with the 4 h cisplatin infusion on days 1 & 2 of treatment Cycles 1 & 2 (Treatment Arms 1, 3) OR Cycles 3 & 4 (Treatment Arms 2, 4);
- **CISplatin** 60 mg/m²/dose infused IV over 4 h on days 1 & 2 (total dose 120 mg/m²/cycle) of treatment cycles 1-4;
- **Pegfilgrastim** 0.1 mg/kg (6 mg for patients weighing ≥45 kg) SC on day 3 or 4 of treatment cycles 1-6;
- **Methotrexate** 12 g/m² (maximum dose 20 g) infused IV over 4 OR 12 h on days 22 & 29 of Cycles 1-4 and on days 15 and 22 of Cycles 5 & 6 (HDMTX infusion duration on Cycles 5 & 6 based on patient tolerance on cycles 1-4);
- **Leucovorin** 15 mg/m² IV or PO every 6 h until serum MTX <0.1 mcM on days 23 and 30 of cycles 1-4 and days 16 & 23 of cycles 5 & 6, **starting 24 h after the start of the HDMTX infusion.**

Intravenous fluid hydration guidelines: Intravenous fluid hydration should be administered prior to, during and after cisplatin and HDMTX. In addition, the urine should be alkalinized to a pH of ≥7 for HDMTX until serum MTX <1 mcM by including sodium bicarbonate or equivalent base in the IV fluids.

Cisplatin:

- Prior to the first dose of cisplatin on day 1 of the cycle, infuse a normal saline (0.9% NaCl) fluid bolus of 750 mL/m² over 1 h.
- Cisplatin is diluted in 0.9% NaCl to a final cisplatin concentration of 100 mg/L. Therefore,

patients will receive 150 mL/m²/h of this solution over the 4 hour drug infusion.

- After the cisplatin infusion is completed, infuse 100 mL/m²/h D₅ 0.45% NaCl + 20 mEq/L KCl until at least 12 h after the second cisplatin infusion is completed and the patient is tolerating PO fluids.
- Monitor Input and Output, at 3hr or 6hr after start of cisplatin
 - If urine Output > total Input by 100 mL/m²/hr over the previous 3 hr, consider 0.9% NaCl bolus (10-15 cc/kg)
 - If total Input > urine Output by 100 mL/m²/hr over the previous 3 hr, consider furosemide (0.5 mg/kg, MAX dose 20 mg) to promote urine output.^{104,105}

HDMTX:

- Prior to the start of a HDMTX infusion, infuse D₅ 0.22% NaCl with 40 mEq/L NaHCO₃ (sodium bicarbonate) or equivalent base as a fluid bolus of 750 mL/m² over 1 h.
- Continue hydration with D₅ 0.22% NaCl with 40 mEq/L NaHCO₃ (sodium bicarbonate) or equivalent base at 100 mL/m²/h until serum MTX <1 mcM and PO fluids are tolerated. Acetate can be substituted if bicarbonate is not available at a 1:1 dose conversion.
- If urine pH <7 administer 0.5 mEq/kg NaHCO₃ IV. Recheck urine pH ≥30 min after NaHCO₃ bolus is complete. Repeat NaHCO₃ bolus until urine pH ≥7 and consider increasing dose of bicarbonate in maintenance fluids if urine pH consistently <7.
- Once urine pH ≥7 start HDMTX infusion. Continue to check urine pH every 8 hours and administer 0.5 mEq/kg NHCO₃ IV if urine pH <7, until serum MTX <1 mcM.
- HDMTX solution (25 mg/mL) is piggy-backed into the hydration fluids and infused over 4 OR 12 h depending on the treatment arm and cycle (see Study Diagram).

Leucovorin dosing guidelines including guidelines for delayed MTX excretion:

- The dose and duration of leucovorin rescue are determined by the plasma MTX concentration. Leucovorin rescue should start no later than 24 h after the **start** of the HDMTX infusion and continue until the plasma MTX concentration is <0.1 mcM.
- **Leucovorin 15 mg/m² IV or PO every 6 h starting 24 h after the start of the HDMTX**

[figure not shown]

Figure 11: Concentration time curves for MTX (12 g/m²) infusions over 4 and 12 h generated by fitting a 2-compartment pharmacokinetic model to the mean plasma MTX concentrations from 1,045 infusions of 12 g/m² over 4 h.⁵

infusion on days 23 and 30 of cycles 1-4 and days 16 & 23 of cycles 5 & 6 and administered until serum MTX <0.1 mcM.

- Serum MTX levels will vary based on the duration of the HDMTX infusion (Figure 11). Table 3 lists the expected plasma MTX concentrations at various times after a 4 and 12 h infusion. **Please contact the PI or study Co-investigators at any time for questions or concerns about MTX levels.**
- If a patient experiences MTX nephrotoxicity and delayed MTX clearance, the leucovorin dose or schedule may need adjustment based on plasma MTX concentration, or the patient may require glucarpidase to lower plasma MTX concentrations. **The study PI or a co-Investigator should be contacted immediately if the plasma MTX concentration is >100 mcM at hour 24, >50 mcM at hour 28-40, or >10 mcM at hour 48 or later. Leucovorin should be escalated to 15 mg/m² IV or PO every 3 h if the plasma MTX concentration is >2-fold higher than expected (Table 3) AND >1 mcM. The every 6 h schedule can be resumed when the plasma MTX concentration is <1 mcM.**

Table 3. Expected MTX levels by infusion duration. (EOI, end of infusion)

Sample time (h)	Plasma MTX [mcM]	
	4 h Infusion	12 h Infusion
EOI	1200	600
24	15	40
36	3	5
48	1	2
60	0.5	1
72	0.3	0.4

96 <0.1 <0.1

3.1.4 Criteria for Starting Treatment

CISplatin/DOXOrubicin (Cycle 1-4) or DOXOrubicin alone (Cycle 5&6):

Delay treatment until the following conditions are met:

- ANC >750/mcL and platelet count >75,000/mcL
- Oral mucositis grade <2
- Hyperbilirubinemia (total) grade <3 and ALT/AST elevation grade <4
- Normal serum creatinine for age and gender (see Table in eligibility criteria) OR creatinine clearance >70 mL/min/1.73 m² (Cycles 1-4 only). If renal function does not recover after a one week delay, administer doxorubicin alone.
- Adequate wound healing (determined by the surgeon) after resection of the primary tumor (prior to Cycle 3) or after resection of pulmonary metastases.

HDMTX:

Delay treatment until the following conditions are met:

- ANC >250/mcL and platelet count >50,000/mcL
- Oral mucositis grade <2
- Hyperbilirubinemia grade <3 and ALT/AST elevation grade <4
- Normal serum creatinine for age & gender OR creatinine clearance >70 mL/min/1.73 m²

Protocol number: CHP12ST051
 Amendment number:
 Version date: April 2, 2013

3.1.5 Dose Modifications

Modification of the doses of cisplatin, doxorubicin, and HDMTX is required if toxicity for the drugs exceeds the thresholds listed in the Tables below on a prior treatment cycle. The percent of full protocol prescribed dose should be recorded on the TDM in the column labeled “% Dose”. If the dose is reduced by 25%, then the % Dose should be recorded as 75% (75% of the full dose).

Cisplatin:

Toxicity	Severity	Modification
Ototoxicity	>30 dB threshold at 2 kHz	Discontinue cisplatin
Nephrotoxicity	Serum creatinine >ULN for age and gender OR creatinine clearance <70 mL/min/1.73 m ²	Hold cisplatin until criterion in Section 3.1.4 is met
Neuropathy*	Grade >2 motor or sensory neuropathy	Hold cisplatin until resolved to grade ≤2

* See Appendix 2 for toxicity grading scale

Doxorubicin:

Toxicity	Severity	Modification
Myelosuppression	Planned day 22 HDMTX is delayed by >10d (cycle day >32) due to ANC <250/mcL or platelet count <50,000/mcL	Reduce doxorubicin dose by 20%
Cardiotoxicity	SF <27% (confirmed with repeat Echocardiogram 1 week later)	Hold doxorubicin until recovery to SF >28%
Mucositis	Grade 4 related to doxorubicin	Reduce doxorubicin dose by 20%

HDMTX:

Toxicity	Severity	Modification
Nephrotoxicity	Serum creatinine >ULN for age and gender OR creatinine clearance <70 mL/min/1.73 m ²	Hold HDMTX. Omit dose if renal function has not recovered after a 7-day delay
Mucositis	Grade 4 related to HDMTX	Reduce HDMTX by 50%

3.1.6 Local Control of Primary Tumor

Complete resection of the primary tumor is the optimal form of local therapy and is performed after two 5-week cycles of neoadjuvant MAP chemotherapy (11 weeks after the start of therapy). A limb salvage procedure is indicated if the neurovascular bundle is not extensively

involved, the tumor can be resected *en bloc* with tumor-free margins, and reconstruction with an endoprosthesis to replace the involved bone and joint is feasible. If a limb salvage procedure is not indicated, an amputation of the involved portion of the limb will be performed.

Radiation therapy is reserved for patients who have unresectable primary tumors (e.g., spine tumors). The timing of radiation therapy will be based on symptoms, such as pain, response to neoadjuvant chemotherapy, and ability to deliver full dose intensity of the chemotherapy regimen. Radiation is less effective than surgery but can achieve local control in some patients.^{106,107}

3.1.7 Management of Metastatic Tumors

Complete resection of overt pulmonary metastases that are present at diagnosis can enhance survival chances.^{11,108} Median sternotomy or bilateral thoracotomies with manual palpation of both lungs is recommended even in patients with unilateral pulmonary metastases on CT scan. Timing of resection of metastatic disease is left to the clinical judgment of the oncologist and surgeons.

3.2 Randomization

Patients will be randomized to one of 4 treatment arms (see Study Diagram), which will determine the order in which they receive pantoprazole with cisplatin (Cycles 1&2 vs. Cycles 3&4) and the order in which they will receive HDMTX as a 4 or 12 h infusion (Cycles 1&2 vs. Cycles 3&4). A block randomization procedure will be used so that 3 of the first 12 subjects will be randomly assigned to each of the 4 treatment arms (three patient per arm) and 3 of subjects 13 to 24 will be randomly assigned to each of the 4 arms (six patients per arm when enrollment is completed). Subjects who are unable to complete 4 cycles of therapy may be replaced, and the new subject will be placed on the same treatment arm as the subject being replaced.

3.3 Study Duration, Enrollment and Number of Sites

3.3.1 Duration of Study

The duration of study participation will be approximately 8 months. The screening process including biopsy of the primary tumor for diagnosis will take up to 2 weeks. The first 4 treatment cycles are 5 weeks each (total, 20 weeks) and cycles 5 and 6 are 4 weeks each (total, 8 weeks). The time for recovery from surgery to resect the primary tumor after Cycle 2 is usually 1-2 weeks. Endpoints for this trial are measured during therapy and at the end of therapy visit after the last HDMTX infusion.

3.3.2 Number of Subjects and Number of Study Sites

This pilot study will be conducted at CHOP. We plan to study 24 subjects. Patients who do not complete 4 cycles of treatment for any reason may be replaced. We may enroll up to 28 subjects in order to have 24 fully evaluable subjects. Based on the number of children with OS seen at CHOP annually, we expect accrual to be complete in 2 to 3 years.

3.4 Study Population

3.4.1 Study Enrollment/Registration

Subjects are enrolled on study after fulfilling the eligibility criteria listed below. Treatment arm will be assigned by the Study PI based on a spreadsheet provided by the Study Biostatistician. Demographic information, results of screening and baseline studies, tumor site(s) and histology, and treatment arm will be entered into OnCore CRM. **Patients must be enrolled and randomized prior to starting neoadjuvant chemotherapy.**

3.4.2 Inclusion Criteria

- **Age:** <30 years of age
- **Diagnosis:** histological diagnosis of high-grade osteosarcoma (Section 3.1.1)
- **Site:** Extremity or central axis (including craniofacial) primary tumor; localized or metastatic
- **Prior therapy:** No prior chemotherapy or radiation therapy for osteosarcoma. Subjects who develop osteosarcoma as a second cancer are eligible if they have not previously received cisplatin, doxorubicin or other anthracyclines, or MTX
- **Kidney function:** Serum creatinine at or below the upper limit of normal (ULN) for age and gender:

Age	Maximum Serum Creatinine (mg/dL)	
	Male	Female
1 mo to < 6 months	0.4	0.4
6 mo to < 1 year	0.5	0.5
1 year to < 2 years	0.6	0.6
2 to < 6 years	0.8	0.8
6 to < 10 years	1	1
10 to < 13 years	1.2	1.2
13 to < 16 years	1.5	1.4
≥ 16 years	1.7	1.4

Derived for Schwartz et al. J Peds 106:522, 1985 utilizing child length and stature data published by the CDC

- **Cardiac function:** Shortening fraction on echocardiogram >28%
- **Hearing:** Hearing level threshold ≤25 dB at all frequencies in both ears to be evaluable for evaluation of pantoprazole's effect on cisplatin ototoxicity. Patients with hearing loss can be enrolled but will not be evaluable for ototoxicity objective.
- **Hematological function:** Absolute neutrophil count >1,000/mcL and platelet count >100,000/mcL

Protocol number: CHP12ST051
 Amendment number:
 Version date: April 2, 2013

3.4.3 Exclusion Criteria

- Receiving H₂ antagonists (cimetidine, ranitidine, famotidine, nizatidine) or proton pump inhibitors (lansoprazole, omeprazole, pantoprazole, esomeprazole, rabeprazole, dexlansoprazole) AND unable to hold the drug for 24 h prior to and 24 h after each cisplatin course on cycles 1-4.
- Inability to tolerate a PPI
- Pregnant or breastfeeding
- Unable to cooperate with research procedures

4. RESEARCH PROCEDURES

Refer to Treatment arm specific TDMs for schedule of drug administration and Schedule of Study Procedures for timing of standard of care and research procedures.

4.1 Research Studies during Treatment

See Schedule of Study Procedures table for timing of standard of care and research procedures.

Test	Specimen	Tube	Volume	Collection	Processing	Storage	Lab/Assay
KIM-1	Spot urine	Urine container	>5 mL	Prior to cisplatin D1, EOI D2, D7; prior to each HDMTX & 24 after the start of infusion; pre-op; C5D1	Centrifuge	-70°C	CTSU Core
NGAL							
NAG							
Cystatin C	Serum	Gold top SST-clot activator	3 mL	Prior to cisplatin and HDMTX; D7; pre-op; C5D1; post-inf IF sCr ≥50% above baseline	Centrifuge	-70°C	UPenn Core
Mg, Cr	Plasma	Light green top	0.5 mL	Prior to cisplatin D1, D2 & D7; C5D1	Send to Clinical Lab	Room temp	Clinical Lab
Mg, Cr	Spot urine	Urine container	>2 mL	Prior to cisplatin D1, D2 & D7; C5D1	Send to Clinical Lab	Room temp	Clinical Lab
BSAP	Serum	Red top	2 mL	Baseline, pre-op, C3D1 & EOT	Clot, centrifuge, separate serum	-70° C	CTSU Core
Pre-albumin	Plasma	Light green top	1 mL	Baseline, D1 C2-6, Pre-op, EOT	Send to Clinical Lab	Room temp	Clinical Lab
MTX	Urine	Conical tube	1 mL	EOI of each HDMTX C1-4	Pipette 1 mL urine into conical tube w/ 9 mL buffer	-70° C	PK Core HPLC/MS/MS

Abbreviations: EOI, end of infusion; Mg, magnesium; Cr, creatinine; BSAP, bone-specific alkaline phosphatase; inf, infusion; EOT, end of therapy; MTX, methotrexate concentration

4.2 Post-Therapy Follow-up

Periodic follow-up and restaging is standard of care for patients who have completed treatment. Guidelines for following patients after completion of treatment are provided in the table below:

Procedure	Months Post-Treatment													
	3	6	9	12	15	18	21	24	30	36	42	48	54	60
History, physical, PS	X	X	X	X	X	X	X	X	X	X	X	X	X	X
CBC, CMP, Mg, PO ₄	X	X	X	X	X	X	X	X						
Chest CT	X	X	X	X	X	X	X	X						
MRI of primary ¹	X	X		X		X		X						
Chest X-ray									X	X	X	X	X	X
X-ray of primary									X	X	X	X	X	X
Bone or PET scan ²		X		X		X		X						
Audiogram				X				X						X
Echocardiogram				X				X		X		X		X
BSAP ³	Draw sample if subject has evidence of tumor recurrence													
Arm circum/Skin fold ³	X	X		X				X		X		X		X

¹ Substitute CT scan if metal in endoprosthesis does not allow for MRI to be performed

² Only if positive for metastatic disease at baseline

³ Research procedure

4.3 Concomitant Medications

H₂-antagonists (cimetidine, ranitidine, famotidine, nizatidine) and **proton pump inhibitors** (lansoprazole, omeprazole, pantoprazole, esomeprazole, rabeprazole, dexlansoprazole) should NOT be administered for 24 h prior to and 24 h after cisplatin on Cycles 1-4. Patients will receive pantoprazole with cisplatin on Cycles 1&2 OR Cycles 3&4.

Probenecid, NSAIDS, sulfonamides (including co-trimoxazole), and penicillins should NOT be administered concurrently with HDMTX. These drugs can interfere with the secretion of MTX by the renal tubule.

Patients should receive **co-trimoxazole** 2.5 mg/kg/dose twice daily on 2 consecutive days per week to prevent pneumocystis pneumonia. Co-trimoxazole should NOT be administered concurrently with HDMTX.

Antiemetics should be administered prior to and as needed during and after chemotherapy according to the CHOP Antiemetic guidelines available on the Cancer Center Website.

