The PK and tolerability of single intravenous doses of 0.8 and 1.6 mg/kg of pantoprazole have been studied in children.³ The C_{max} and AUC of IV pantoprazole at 0.8 and 1.6 mg/kg in children aged 2 to 16 years were similar to these PK parameters in adults at 40 and 80 mg (Figure 8). The clearance of pantoprazole in children was 0.2 L/h/kg and the half-life was 1.2 h. Although the t_{1/2} is short, its pharmacodynamic effect is more long lasting.⁹⁴ PPIs interfere with MTX excretion,⁹⁸ but by 20 days after the last cisplatin dose when HDMTX is administered, pantoprazole will be completely cleared.

[figure not shown]

Figure 8 PK of intravenous pantoprazole in children (2-16 yrs) at doses of 0.8 and 1.6 mg/kg compared to adults at 20, 40 and 80 mg.^{3,4}

Pantoprazole is primarily metabolized by CYP2C19, which is genetically polymorphic. CYP2C19 activity is absent in 3% of whites and 20% of Asians, and children with CYP2C19 polymorphisms have slower clearance and longer t_{1/2}.³

The single IV doses of pantoprazole (0.8 and 1.6 mg/kg) were well tolerated. Three adverse events occurred in 18 patients, all of which were mild and judged to be unrelated to pantoprazole.³ The most common toxicities associated with PPIs are diarrhea, nausea, headaches, abdominal pain, fatigue and dizziness.⁹⁴

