9.3.2 Risk assessment

There is risk associated with the addition of pantoprazole to cisplatin therapy, however PPIs are widely used in pediatric medicine and there is substantial experience with the toxicities associated with these agents (Section 7.1, Adverse Events). Single IV doses of pantoprazole are very well tolerated in children. An association between the use of PPIs and *C. difficile* colitis was recently reported, but the use of pantoprazole in this study is limited to 4 doses. The use of cisplatin and pantoprazole together has not been studied in children. As described in the background, we do not expect pantoprazole to alter the excretion of cisplatin. PPIs are frequently administered chronically to patients receiving chemotherapy for symptoms of reflux. The risk associated with administration of pantoprazole with cisplatin must be considered greater than minimal.

Prolonging the infusion duration may alter the toxicity profile of HDMTX because the pharmacologic effect of MTX is determined by the duration of exposure to the drug. Leucovorin rescue will start 24 h after the start of the HDMTX infusion for both infusion durations. The PK simulations (Figure 4) show that plasma concentrations at later time points are similar for the two infusion durations. There is considerable experience

Protocol number: CHP12ST051
Amendment number:
Version date: April 2, 2013

demonstrating tolerability of HDMTX in children with leukemia treated with higher doses of MTX (e.g., 33 g/m²) administered as prolonged infusions with leucovorin rescue. Administration of 12 g/m² HDMTX infused over 12 h instead of 4 h must be considered greater than minimal risk.

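### The protocol says PPIs interfere with methotrexate excretion, but its list of drugs barred with high-dose methotrexate omits them, so none of the 12 doses is protected from non-study PPI use

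*Combined protocol and SAP*

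**What the plan says.** Section 1.3.5 states that "PPIs interfere with MTX excretion". It then deals with the study drug alone, on the ground that "by 20 days after the last cisplatin dose when HDMTX is administered, pantoprazole will be completely cleared".

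Section 4.3 has two separate rules:

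- Around cisplatin, H2 antagonists and PPIs "should NOT be administered for 24 h prior to and 24 h after cisplatin on Cycles 1-4".
- Around HDMTX: "Probenecid, NSAIDS, sulfonamides (including co-trimoxazole), and penicillins should NOT be administered concurrently with HDMTX". The reason given is: "These drugs can interfere with the secretion of MTX by the renal tubule". PPIs do not appear here.

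The exclusion criteria in section 3.4.3 match the first rule only. A patient already on a PPI is excluded if "unable to hold the drug for 24 h prior to and 24 h after each cisplatin course on cycles 1-4", and may otherwise enrol.

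Section 9.3.2 says that "PPIs are frequently administered chronically to patients receiving chemotherapy for symptoms of reflux".

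Section 3.1.3 schedules methotrexate "on days 22 & 29 of Cycles 1-4 and on days 15 and 22 of Cycles 5 & 6".

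**The concern.** The protocol names a hazard in its background and leaves it out of the operational rule that exists to control such hazards. No section authorises a PPI with HDMTX, but none forbids it. Section 4.3 names PPIs for cisplatin and then gives a separate HDMTX list without them, so a clinician could reasonably conclude that a PPI may restart once the cisplatin window has passed.

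The main stake is safety. Section 1.3.2.1 explains that delayed methotrexate excretion produces sustained plasma levels that leucovorin may not rescue effectively, and worsens the drug's other toxicities. It adds that longer leucovorin rescue can weaken the antitumour effect. It also reports delayed excretion in 5% of the centre's HDMTX courses in 2011.

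The second stake is smaller. Plasma and urine methotrexate and the kidney-injury markers are primary endpoints (section 5.1). PPI use that comes and goes between doses could add variability to them.

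**Working it through.** This is a check of the schedule and of which rules cover which doses. No power formula applies.

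**Inputs**

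- HDMTX: days 22 and 29 of cycles 1-4; days 15 and 22 of cycles 5-6 (section 3.1.3).
- Cisplatin: 4 h infusions on days 1 and 2 of cycles 1-4 only (section 3.1.3).
- Cycle length: 35 days for cycles 1-4, 28 days for cycles 5-6 (section 3.1.3).
- PPI hold: 24 h before to 24 h after cisplatin, cycles 1-4 (sections 3.4.3 and 4.3).
- Expected time to methotrexate below 0.1 mcM: 96 h for both infusion durations (Table 3).
- Pantoprazole half-life: 1.2 h (section 1.3.5).
- Planned patients: 24 (section 3.3.2).

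**The plan's own figures reproduce**

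- Infusions in the crossover part: 4 cycles × 2 = 8, matching the n=8 in section 5.3.
- Gap from last cisplatin dose to first HDMTX dose: day 22 − day 2 = 20 days, as section 1.3.5 says.
- That gap is 20 × 24 / 1.2 = 400 half-lives, so study pantoprazole is not the problem.

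**Doses at issue**

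- Per patient: 4 × 2 + 2 × 2 = 8 + 4 = 12.
- In 24 patients: 24 × 8 = 192 doses in the primary comparison and 24 × 12 = 288 overall. These count doses without a rule, not doses actually given with a PPI.
- One patient taking a PPI throughout cycles 1-4 would contribute up to 8 exposed primary doses, 8/192 = 4.2%, with 4 at each infusion duration.

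**Does the cisplatin hold reach any HDMTX dose?**

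Take the start of day 1 cisplatin as hour 0. The day 2 infusion runs from hour 24 to hour 28, so the hold runs from hour −24 to hour 28 + 24 = 52. That is 76 h, or 3.2 days, ending on day 3.

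| HDMTX dose | Days since hold ended | Days until next hold starts |
|---|---|---|
| Cycles 1-4, day 22 | 22 − 3 = 19 | 13 (cycles 1-3) |
| Cycles 1-4, day 29 | 29 − 3 = 26 | 6 (cycles 1-3) |
| Cycles 5-6, days 15 and 22 | no hold in these cycles | none |

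No further hold follows cycle 4, and the surgery gap after cycle 2 only lengthens the interval there. Even with a 96 h clearance window added after each dose, the hold overlaps 0 of 12 doses.

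**Burden of a hold around HDMTX**

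As an example, hold from 24 h before the infusion until expected clearance at 96 h.

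- Per dose: 24 + 96 = 120 h. Two doses per cycle: 240 h = 10 days.
- Cycles 1-4: the holds run from hour 480 to 600 and from hour 648 to 768, overlapping neither each other nor the cisplatin hold. The total off PPI is 76 + 240 = 316 h = 13.2 of 35 days (38%).
- Cycles 5-6: 10 of 28 days (36%).

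**The case against.** The strongest reply accepts the gap and disputes its weight.

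- **Size unknown.** The 192 and 288 are opportunities for exposure. The documents give no PPI-use rate and no interaction size, and section 9.3.2 speaks of chemotherapy patients in general. This stands: neither exposure nor added risk can be estimated.
- **The comparison is largely protected.** A chronic user has 4 exposed doses at each duration, and section 6.1.1 specifies a subject-level random intercept. A stable additive PPI effect would largely cancel in the within-patient contrast. This also stands. Only intermittent use, or a PPI effect that differs between the 4 h and 12 h infusions, could disturb the comparison.
- **Monitoring is strong.** Methotrexate and creatinine are measured at the end of infusion, at hour 24 and then daily until methotrexate is below 0.1 mcM. Leucovorin is adjusted to the level, glucarpidase is available, and renal function is checked before each dose (Schedule of Study Procedures; sections 3.1.3 and 3.1.4). This limits the consequences but does not prevent the interaction. The protocol has all this monitoring and still bars four drug groups.
- **Mechanism.** Section 4.3 gives tubular secretion as its reason, whereas section 1.3.5 says only excretion. The wording does differ. However, the reference cited in section 1.3.5 is, by its title, about delayed methotrexate elimination with PPIs in high-dose therapy, which is the outcome the list exists to avoid.
- **The remedy goes further than the existing rule**, which bars drugs given concurrently and sets no window. That is fair, so the 24 h lead-in is offered only as an example.

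**Conclusion.** The concern holds. The protocol states that PPIs impair methotrexate excretion, admits PPI users, describes chronic use as frequent, and prohibits PPIs at 0 of 12 HDMTX doses per patient, including all 8 in the primary comparison. Followed as written, it allows a combination that its own background warns about.

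This is primarily a safety gap that should be closed; it is not a flaw in the analysis. The dose count assumes the planned schedule with no delays or omitted doses. Clinicians may already hold PPIs under local practice, but the protocol does not require it.

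**What to change.** 1. Add PPIs to the section 4.3 list of drugs not to be given with HDMTX.
2. Define the hold, for example from 24 h before each infusion (matching the cisplatin hold) until methotrexate is below 0.1 mcM. The investigators may choose another lead-in.
3. Record any PPI use at each HDMTX dose. The history and physical examination already scheduled on every HDMTX day is a convenient place.

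Leave the eligibility criteria and the primary model unchanged.

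The cost is one sentence and one data field. The real downside falls on chronic PPI users, who under the example hold would be off the drug about 13 of 35 days in cycles 1-4 and 10 of 28 days in cycles 5-6, or longer if clearance is delayed. Some will need another reflux treatment around HDMTX. Section 4.3 restricts H2 antagonists only around cisplatin, so the protocol does not rule those out.
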